### **7.1.1 Liver Chemistry Stopping Criteria**

Refer to [Section 8.3.7.7](#) for hepatic criteria for IP interruption or discontinuation.

Discontinuation of IP because of clinically significant abnormal liver test results should be considered by the investigator in consultation with the medical monitor when a participant meets one of the conditions presented in [Section 7.1](#), or in the presence of abnormal liver chemistries not meeting protocol-specified stopping rules if the investigator believes that it is in best interest of the participant.

### **7.1.2 Temporary Interruption of Investigational Product**

Some possible reasons for temporarily withholding the IP include, but are not limited to:

- Serious or opportunistic infections ([Section 5.2](#) and [Appendix 15.3](#)). The IP is to be withheld until resolution of all acute clinical signs and symptoms, and completion of all appropriate anti-infective treatment.
- HBV DNA results are reported as positive, or as detecting HBV DNA, but HBV DNA is below the level of quantification. The sponsor's designated medical monitor should be contacted regarding study status of the participant. HBV DNA testing is to be repeated as soon as is feasible. If HBV DNA is confirmed as positive, the participant must be permanently discontinued from IP ([Section 7.2.1](#)).
- Hepatic event abnormalities are presented in [Section 8.3.7.6](#).
- Liver test abnormalities are presented in [Section 8.3.7.7](#).

## 7.2 Withdrawal From the Study

Participants may withdraw from the study at any time and for any reason without prejudice to their future medical care by the investigator or at the study site. The investigator should discontinue a participant from the study if they think that continuation would be detrimental to the participant's well-being.

The investigator must withdraw a participant from the study if the participant is known to be pregnant.

Withdrawal from the study is expected to be uncommon. If the participant is unwilling or unable to remain in the study, the participant will complete procedures for an early discontinuation (termination) visit and posttreatment follow-up, if applicable.

Refer to the SoA ([Table 1-1](#)) for data to be collected at the time of discontinuation of the IP and follow-up and for any further evaluations that need to be completed.

The reasons for participants withdrawing from the study, based on the judgment of the investigator and/or the sponsor, will be recorded. At the discretion of the investigator, a participant may withdraw from the study for any of the following reasons:

### Investigator Decision

1. The investigator decides that the participant should be withdrawn from the study. Some examples may include:
  - Intercurrent illness that would, in the opinion of the investigator, affect assessments of clinical status to a significant degree;
  - Treatment-related AEs that are clinically significant, deemed persistent, in the opinion of the investigator;
  - Unacceptable toxicity occurred; or
  - The investigator or sponsor decided to withdraw their participation in the study.

### Participant Decision

1. The participant was unwilling or unable to comply with the protocol.
2. The participant enrolled into another interventional clinical study in which an

investigational treatment or approved therapy for investigational use is administered.

3. The participant was lost to follow-up.
4. The participant withdrew consent.

Although a participant is not obliged to give their reason(s) for withdrawal from the study, the investigator should make every effort to ascertain the reason(s) while fully respecting the participant's rights.

### **7.2.1 Mandatory Withdrawal From the Study**

The following are findings requiring permanent discontinuation and withdrawal from the study if a participant develops any of the following conditions during the study:

- Malignancy (except for successfully treated basal or squamous cell skin carcinoma)
- Serious or opportunistic infection that in the opinion of the investigator merits the study treatment being discontinued. Such infections may include, but are not limited to:
  - HIV/AIDS infection
  - Active TB infection or untreated latent TB infection
  - HCV RNA positive
  - HBV DNA positive: The HBV DNA result is to be confirmed if initial positive test result is positive but below the level of quantification. The participant is to be referred to, evaluated, and managed by a specialist physician with expertise in evaluation and management of viral hepatitis prior to discontinuation of any immunomodulatory and/or immunosuppressive therapy, including study treatment. Timing of discontinuation from study treatment relative to the initiation of any antiviral treatment for hepatitis is to be based on the recommendation of the consulting specialist physician, in conjunction with the investigator, and aligned with medical guidelines and standard-of-care.

### **7.2.2 Withdrawal of Inadvertently Enrolled Participants**

If the sponsor or investigator identify a participant who did not meet enrollment criteria and was inadvertently enrolled, then the participant must be discontinued from the study unless there are circumstances that make it medically necessary for the participant to continue on study treatment. If the investigator and the sponsor-designated medical monitor agree it is medically appropriate to continue, the investigator must obtain documented approval from the sponsor-designated medical monitor to allow the inadvertently enrolled participant to continue in the study.

### **7.3 Lost to Follow-up**

A participant will be considered lost to follow-up if he or she repeatedly fails to return for scheduled visits and is unable to be contacted by the study site.

The following actions must be taken if a participant fails to return to the study site for a required study visit:

- The study site must attempt to contact the participant and reschedule the missed visit as soon as possible and counsel the participant on the importance of maintaining the assigned visit schedule and ascertain whether the participant wishes to and/or should continue in the study.
- Before a participant is deemed lost to follow-up, the investigator or designee must make every effort to regain contact with the participant (where possible, 2 telephone calls and, if necessary, a certified letter to the participant's last known mailing address or local equivalent methods). These contact attempts should be documented in the participant's medical record.

If the participant continues to be unreachable, he/she will be considered to have withdrawn from the study.

## **8 Study Assessments and Procedures**

It is recommended that assessments/procedures completed at study site visits be performed in the following order as applicable:

1. Collection of AEs, concomitant medication

2. Measurement of vital signs and weight
3. PRO completion
4. Nasal peak inspiratory flow (NPIF) and spirometry
5. Endoscopy (NPIF and spirometry should be performed prior to endoscopy)
6. Laboratory sample collection – blood and urine
7. IP administration

Study assessments and procedures and their timing are summarized in the SoA ([Table 1-1](#)). Protocol waivers or exemptions from assessments or procedures are not allowed. Adherence to the study design requirements, including those specified in the SoA, is essential and required for study conduct.

In the event of a significant study-continuity issue (eg, caused by a pandemic), alternate strategies for participant visits, assessments, medication distribution, and monitoring may be implemented by the sponsor or the investigator, per local regulatory agency/ethics requirements ([Appendix 15.6](#)).

Repeat or unscheduled laboratory samples may be obtained for safety reasons or for technical issues with the samples.

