### **8.2.17 Patient Global Impression of Severity/Patient Global Impression of Change**

Patient Global Impression of Severity (PGI-S) and Patient Global Impression of Change (PGI-C) scales will be collected to facilitate the assessment of clinically meaningful within-participant change for nasal congestion, loss of smell, and postnasal drip. The PGI-S and PGI-C will be collected on a tablet at the study site per the SoA ([Table 1-1](#) and [Section 10.1.1](#)).

The PGI-S: nasal congestion asks the participant to rate the overall severity of their nasal congestion due to chronic rhinosinusitis over the past 14 days with response options of: no symptoms, mild, moderate, severe, and very severe.

The PGI-S: loss of smell asks the participant to rate the overall severity of their loss of smell due to chronic rhinosinusitis over the past 14 days with response options of: no symptoms, mild, moderate, severe, and very severe.

The PGI-S: postnasal drip asks the participant to rate the overall severity of their postnasal drip due to chronic rhinosinusitis over the past 14 days with response options of: no symptoms, mild, moderate, severe, and very severe.

The PGI-C: nasal congestion asks the participant to describe the overall change in their nasal congestion due to chronic rhinosinusitis since they started taking the new medication with response options of very much better, much better, a little better, no change, a little worse, much worse, and very much worse.

The PGI-C: loss of smell asks the participant to describe the overall change in their loss of smell due to chronic rhinosinusitis since they started taking the new medication with response options of very much better, much better, a little better, no change, a little worse, much worse, and very much worse.

The PGI-C: postnasal drip asks the participant to describe the overall change in their postnasal drip due to chronic rhinosinusitis since they started taking the new medication with response options of very much better, much better, a little better, no change, a little worse, much worse, and very much worse.

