### **8.3.1.2 Eliciting and Documenting Adverse Events**

AEs will be assessed from the time the participant signs the ICF and up until participation in the study has ended.

If the investigator learns of any SAE, including a death, at any time after a participant has been discharged from the study, and he/she considers the event to be reasonably related to the study treatment or study participation, the investigator must promptly notify the sponsor.

All SAEs that occur during the study through the end of the follow-up period must be reported, even if not related to study treatment.

At every study visit, participants will be asked a standard nonleading question to elicit any medically-related changes in their well-being. Investigators and study site staff will take care to avoid introducing bias when detecting events. Open-ended and nonleading verbal questioning of the participant is the preferred method to inquire about event occurrences.

In addition to participant observations, AEs identified from any study data (eg, laboratory values, physical examination findings) or identified from review of other documents (eg, participant diaries) that are relevant to participant safety will be documented on the AE page in the eCRF.

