### 10.1.1 Electronic Data Capture of Clinical Outcome Assessment

All PROs conducted at the study site will be captured on an electronic tablet during study site visits. All PRO assessments captured away from the study site will be captured in the participants' eDiaries.

The tablets at the study site will be programmed to capture the following PROs, which will be completed by participants during study site visits according to the SoA ([Table 1-1](#)):

- VAS of CRS severity ([Section 8.2.9](#))
- PGI-S scales ([Section 8.2.17](#))
- PGI-C scales ([Section 8.2.17](#))
- SNOT-22 ([Section 8.2.10](#))
- ACQ-6 ([Section 8.2.12](#), in asthma participants only)
- PROMIS Short Form v1.0 – Anxiety 8a ([Section 8.2.16.1](#))
- PROMIS Short Form v1.0– Depression 8a ([Section 8.2.16.2](#))
- WPAI+CIQ:CRSwNP ([Section 8.2.15](#))
- EQ-5D-5L ([Section 8.2.14](#))

The PROs will be completed by participants using an on-site tablet in the following order: VAS of CRS severity, PGI-S: nasal congestion, PGI-S: loss of smell, PGI-S: postnasal drip, PGI-C: nasal congestion, PGI-C: loss of smell, PGI-C: postnasal drip, SNOT-22, ACQ-6, PROMIS Anxiety, PROMIS Depression, WPAI+CIQ:CRSwNP, and EQ-5D-5L.

The eDiaries will be programmed to capture the following PROs and other study data:

- NCS ([Section 8.2.1](#))
- Loss of smell ([Section 8.2.5](#))
- Postnasal drip ([Section 8.2.6](#))

- Loss of taste ([Section 8.2.8](#))
- Facial pain/pressure ([Section 8.2.8](#))
- Rhinorrhea ([Section 8.2.8](#))
- IP dosing diary ([Section 6.1.2](#))
- Background medication dosing diary ([Section 6.10.2.2](#))

The PROs should be completed by the participant in their eDiary in the following order: NCS, loss of smell, postnasal drip, loss of taste, facial pain/pressure, and rhinorrhea.

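### The recommended visit order puts the adverse-event and medication interview ahead of the tablet questionnaires; moving the questionnaires to first place removes an avoidable source of priming

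*Protocol*

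**What the plan says.** Section 8 opens with "It is recommended that assessments/procedures completed at study site visits be performed in the following order as applicable", followed by seven steps. The first three are "Collection of AEs, concomitant medication", "Measurement of vital signs and weight" and "PRO completion". NPIF with spirometry, endoscopy, laboratory samples and dosing come after.

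Section 8.3.1.2 describes the adverse-event interview: at every study visit "participants will be asked a standard nonleading question to elicit any medically-related changes in their well-being". It prefers open-ended, nonleading questions and asks staff to avoid introducing bias.

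Section 10.1.1 states "All PROs conducted at the study site will be captured on an electronic tablet during study site visits" and fixes the sequence of the questionnaires among themselves ("The PROs will be completed by participants using an on-site tablet in the following order: VAS of CRS severity, PGI-S: nasal congestion", and so on). It does not say where the set as a whole sits relative to the interview. Section 8.2.17 says that PGI-S and PGI-C "will be collected to facilitate the assessment of clinically meaningful within-participant change" in nasal congestion, loss of smell and postnasal drip.

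**The concern.** Questionnaires that ask how troublesome symptoms are, or how much has changed since the new medication began, are best completed before anyone discusses the participant's health. Here the recommended order does the reverse.

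The interview may also extend past one neutral question. A reported event of special interest prompts the site to collect additional data (Section 8.3.1.1.5). Injection site reactions call for further characterization (Section 8.3.7.3). Every infection, including a common cold, needs its own page (Section 8.3.7.11). A participant may thus talk about an upper-airway illness shortly before scoring sino-nasal symptoms.

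If such conversations are more frequent in one arm, the priming is not shared equally. Section 2.3.2 names keratitis, injection site reactions, conjunctivitis and herpes zoster as known reactions to lebrikizumab, so unequal reporting is plausible. What is at stake is the cleanness of the site-based patient-reported comparisons, and of the PGI ratings used to interpret change.

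**Working it through.** The point concerns sequence, so there is no figure to reproduce. The check sets the Section 8 order against the Schedule of Activities (Table 1-1) and the sections on data capture and analysis.

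**1. Does the interview occur at every questionnaire visit?** Yes. Table 1-1 schedules adverse events and concomitant medications at every visit, including unscheduled ones.

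**2. Which instruments follow it?** All nine tablet instruments listed in Section 10.1.1: CRS VAS, PGI-S, PGI-C, SNOT-22, ACQ-6, PROMIS Anxiety, PROMIS Depression, WPAI+CIQ and EQ-5D-5L.

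**3. How often, and is there a step in between?** Table 1-1 schedules vital signs after baseline at Visits 5, 9, 10 and 11 of the treatment period, but not at Visits 4, 6, 7 or 8. At those four visits step 2 is empty and the questionnaires follow the interview directly.

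| Instrument | Scheduled post-baseline treatment visits | Of these, with no vital signs in between |
|---|---|---|
| PGI-S | 8 (Visits 4 to 11) | 4 (Visits 4, 6, 7, 8) |
| CRS VAS | 5 (Visits 4, 5, 7, 9, 11) | 2 (Visits 4, 7) |
| SNOT-22 | 5 (Visits 5, 7, 9, 10, 11) | 1 (Visit 7) |
| ACQ-6 (asthma only) | 3 (Visits 5, 9, 11) | 0 |
| PGI-C | 2 (Visits 9, 11) | 0 |
| EQ-5D-5L, WPAI+CIQ, PROMIS (both forms) | 2 each (Visits 9, 11) | 0 |

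These counts show how often the sequence arises. They do not measure bias.

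**4. Does any other section reverse the order?** No. Section 10.1.1 orders only the questionnaires. Sections 6.10.3 and 8.2.7 ask for them before rescue treatment, which addresses a different problem.

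**5. Does anything need the interview to come first?** The document gives no such reason. Dosing is step 7, so adverse-event collection would still precede it if the questionnaires moved up.

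**6. Which endpoints are reached?** Table 3-1 places all nine instruments among the other secondary endpoints. Section 9.5.5 has these interpreted descriptively, with comparative results and confidence intervals reported. Section 9.8 leaves them outside multiplicity control. Nasal congestion, loss of smell and postnasal drip are daily diary items captured away from the site (Sections 8.2 and 10.1.1). The polyp score is read centrally by blinded assessors (Section 8.2.2). The other key secondary endpoints (Lund Mackay score, FEV1, rescue events) are not questionnaires.

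**The case against.** The strongest reply is that nothing here is wrong on its face. The order is recommended, as applicable, so a site may start with the tablet without deviating. The interview is open-ended and nonleading. At Visits 9 and 11, the only scheduled PGI-C visits, vital signs intervene, taken after at least 5 minutes seated (Section 8.3.5). The sequence is the same in every arm and also applies at baseline, so a constant priming effect would largely cancel from change scores and from the contrast between arms. The preference for questionnaires first comes from general practice, not from this document.

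Much of this stands, and it is why the point is minor. Two parts do not answer it. A recommended order is the one sites can be expected to follow. And the shared baseline sequence cancels only the constant part of any priming: events that arise after dosing starts are not discussed at baseline, and PGI-C has no baseline.

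A reader might infer more than the text supports:

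- *That participants are run through a list of side effects.* Section 8.3.1.2 describes no checklist.
- *That the interview reveals treatment assignment.* For adults the staff are blinded (Section 6.4), and a participant with conjunctivitis or an injection site reaction already knows about it. Discussion can bring an event to mind, but the order does not break the blind.
- *That the co-primary results are biased.* Neither co-primary score is collected in this sequence. The co-primary analysis compares means (Table 9-3) and uses no PGI-derived threshold, so the PGI scales bear only on interpretation.
- *That the adolescent cohort makes the matter worse.* That cohort is open-label and summarized descriptively without hypothesis tests (Section 9), so there is no blind to compromise and no arm contrast to distort.

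**Conclusion.** The recommended order places an avoidable prompt ahead of nine subjective instruments, and the document gives no reason for doing so. It can prime ratings in all arms alike. It would distort a treatment contrast only if adverse-event reporting differed by arm and the discussion changed how participants rated themselves. Both are assumptions: Section 2.3.2 makes the first plausible, and nothing in the document bears on the second.

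The size is unknown and probably small. The reach is limited to descriptive other secondary outcomes and to PGI-S and PGI-C as aids to interpretation. No co-primary or key secondary result depends on it. It is worth changing because the change costs almost nothing.

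**What to change.** In the Section 8 recommended order, make completion of the tablet questionnaires step 1, ahead of adverse-event and concomitant-medication collection and any other procedure. Keep the remaining steps in their present sequence, and keep the questionnaire order in Section 10.1.1 as it is. Adverse-event collection still comes well before dosing.

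The cost is one moved line, the matching change in site instructions and a short reminder to sites. No visit, procedure or staff time is added. If the change is made after enrollment has begun, some participants will have a baseline under one order and later visits under the other. That applies to all randomized arms alike, and the date of the change should be recorded.

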## **8.1 Administrative, Screening, and Baseline Procedures and Assessments**

Adherence to the study design requirements, including those specified in the SoA ([Table 1-1](#)), is essential and required for study conduct.

All screening evaluations must be completed and reviewed to confirm that potential participants meet all eligibility criteria. The investigator will maintain a screening log to record details of all participants screened and to confirm eligibility or record reasons for screening failure, as applicable.

### **8.1.1 Informed Consent and Assent Procedure**

The procedural requirements of the informed consent and assent are described in [Section 11.3](#).

## 8.1.2 Demographics, Medical History, and Prior Medication Procedure

Demographic information to be obtained will include age, sex, race, and ethnicity as described by the participant, and substance use history. The scientific rationale for this collection is the need to assess variable response in safety and/or efficacy based on race or ethnicity. Substance use history will also be collected. Only if all relevant data are collected can this assessment be made.

Medical history to be obtained will include determining whether the participant has any significant conditions or diseases relevant to the disease under study that stopped at or prior to signing the ICF. Ongoing conditions are considered concurrent medical conditions.

Medication history (ie, prior medications) to be obtained includes any medication relevant to eligibility criteria and safety evaluation stopped at or within the specified period of time prior to screening (Visit 1).

Physical examination (including height) is described in [Section 8.3.3](#) and [Section 8.3.4](#).

Assessment of vital signs (including weight) is described in [Section 8.3.5](#).

## 8.2 Efficacy Assessments

Each participant's CRSwNP will be assessed as specified in the SoA ([Table 1-1](#)).

Electronic clinical outcome assessments (eCOAs) will be completed by participants using an eDiary and an on-site tablet ([Table 1-1](#) and [Section 10.1.1](#)). The eDiary will be completed by participants around the same time each day (preferably in the morning) starting from run-in (Visit 2), and participants will be asked to record the severity of their nasal congestion, loss of smell, postnasal drip, loss of taste, facial pain/pressure, and rhinorrhea at its worst for the previous 24 hours using their eDiaries ([Section 8.2.1](#), [Section 8.2.5](#), [Section 8.2.6](#), and [Section 8.2.8](#)). Adolescent participants should enter their responses into the ePRO devices (eDiary and tablet) independently but may have parental supervision if needed.

